8.3. Precautions for Concomitant Medications, Food, and Surgical Intervention

The bioavailability and in consequence the safety as well as efficacy profile of the study drug may be altered when co-administered with medications or food listed in [Table 26](#). Therefore, these medications should be avoided, or should be administered with caution concomitantly with study therapy. Guidance for surgical intervention is also provided in this table.

Based on in vitro data, erdafitinib is metabolized by cytochrome CYP2C9 and CYP3A4. A clinical drug-drug interaction study showed that on average, erdafitinib exposure (C_{max} and AUC) was increased 5% to 34% when co-administered with itraconazole (a strong inhibitor of CYP3A4) and 21% to 49% when co-administered with fluconazole (a moderate inhibitor of CYP2C9). For this reason, strong CYP3A4 and moderate CYP2C9 inhibitors should be used with caution (see [Attachment 4](#)). Consider alternative therapies that are not strong inhibitors of CYP3A4 or moderate inhibitors of CYP2C9 during treatment with erdafitinib. If co-administration of these drugs is unavoidable, monitor the subject closely for adverse reactions and consider dose modifications accordingly. If the strong inhibitor of CYP3A or moderate inhibitor of CYP2C9 is discontinued, the erdafitinib dose may be increased up to the maximum of 9 mg daily in the absence of drug-related toxicity.

The impact of moderate CYP2C9 inducers and strong CYP3A inducers (such as rifampin) on erdafitinib was not clinically studied. Co-administration of erdafitinib with these agents may significantly decrease erdafitinib exposure. Therefore, the concomitant use of these agents with erdafitinib should be avoided (see [Attachment 4](#)). Co-administration of erdafitinib with moderate CYP3A inducers may decrease erdafitinib exposure. Caution should be exercised for concomitant administration of erdafitinib and moderate inducers of CYP3A4 (see [Attachment 4](#)).

Erdafitinib was shown to inhibit, in in vitro experiments, human P-glycoprotein (P-gp) at the concentrations achieved at therapeutic doses in humans. If co-administration of erdafitinib with P-gp substrates is unavoidable, separate erdafitinib administration by at least 6 hours before or after administration of P-gp substrates with narrow therapeutic index (<https://www.fda.gov/downloads/drugs/guidances/ucm292362.pdf>); in addition, drugs with a narrow therapeutic index should only be used when the benefit outweighs the potential risk.

Table 26: Concomitant Medications and Surgical Interventions to be Avoided or to be Used With Caution

Moderate CYP2C9 inducers and strong CYP3A inducers

 Co-administration of erdafitinib with these agents may significantly decrease erdafitinib exposure. Therefore, the concomitant use of these agents with erdafitinib should be avoided.
Moderate or strong CYP2C9 and CYP3A inhibitors, moderate CYP3A inducers

 Moderate or strong in vivo inhibitors of CYP3A and CYP2C9 enzymes should be used with caution¹ Moderate in vivo inducers of CYP3A enzyme¹ should be used with caution
QT-Prolonging Agents

 Medications known to cause Torsades de Pointes²
P-gp Substrates

 P-gp substrates with narrow therapeutic index (eg, digoxin)
Medications Known to Increase Serum Levels of Phosphate

 Phosphate supplements (oral or IV), vitamin D supplements, antacids, and phosphate-containing enemas & laxatives (oral/rectal)

Surgical Intervention

• Held at least 3 to 7 days pre- and post-surgery depending upon the type of surgery and the risk of bleeding

Abbreviations: P-gp = P-glycoprotein

1. For a listing of CYP3A and CYP2C9 inhibitors and inducers see [Attachment 4](#).
2. For a listing of medications that cause QT prolongation see http://www.acert.org/medical-pros/drug-lists/list-01.cfm?sort=Generic_name.

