Two new regimens will be explored where erdafitinib and cetrelimab will be combined with either cisplatin or carboplatin. In the Phase 1b erdafitinib + cetrelimab + platinum chemotherapy cohort, the doses of erdafitinib (8 mg daily, no up-titration) and cetrelimab (360 mg every 3 weeks [Q3W]) are constant, while doses of cisplatin and carboplatin may be adjusted based on dose-limiting toxicity as described in the protocol and within the range of acceptable doses in the prescribing information (US prescribing information, EU SmPC, or equivalent for the region/country).

Erdafitinib + cetrelimab + cisplatin (erdafitinib + cetrelimab + cis) cohort:

First line subjects with or without select FGFR alterations will receive erdafitinib and cetrelimab in combination with cisplatin. The starting dose level of cisplatin will be 50 mg/m² administered intravenously on Day 1 of a 3-week cycle (DL2C). If the mTPI-2 criteria for escalation are met in DL2C, the dose of cisplatin will be increased to 60 mg/m² (DL2C1). The DLT period for dosing level DL2C and DL2C1 will be 2 cycles (6 weeks/42 days).

Erdafitinib + cetrelimab + carboplatin (erdafitinib + cetrelimab + carbo) cohort:

First line subjects with or without select FGFR alterations will receive erdafitinib and cetrelimab in combination with carboplatin. The starting dose of carboplatin (AUC4 mg/mL/min) administered intravenously on Day 1 of a 3-week cycle (DL2D). If the mTPI-2 criteria for escalation are met in DL2D, the dose of carboplatin will increase to AUC5 mg/mL/min with a maximum dose of 750 mg (DL2D1). The DLT period for dosing level DL2D and DL2D1 will be 2 cycles (6 weeks/42 days).

Phase 2 (Dose Expansion): (APPENDIX 3: PHASE 2 ERDAFITINIB +/- -CETRELIIMAB)

Two dosing arms may be explored: Arm A and Arm B

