6.2.1. Dose Up-titration Guidelines

Based on emerging safety data, on 12 May 2020, the DRC recommended to remove the requirement for up-titration from the erdafitinib + cetrelimab combination in Arm B. The DRC also made a recommendation to close Dose level 2 in Phase 1b and focus enrollment efforts into the Phase 2 part of the study. Therefore, DL2 will be closed. DL2B will remain open and will include up-titration of erdafitinib based on serum phosphate concentration from a blood sample on Day 15 and the absence of significant erdafitinib-related toxicity on C1D15 as determined by the investigator.

Subjects assigned to Dose Level DL2 or DL2B in Phase 1b or Arm A and in Phase 2, will be assigned to the up-titrated dose level of erdafitinib based on serum phosphate concentration from a blood sample on Day 15 and the absence of significant erdafitinib-related toxicity on C1D15 as determined by the investigator. There is no up-titration in either of the erdafitinib + cetrelimab + platinum (cisplatin or carboplatin) chemotherapy cohort or Arm B of the Phase 2 erdafitinib +/- cetrelimab cohort.

- Subjects with serum phosphate levels higher than 9.00 mg/dL (>2.91 mmol/L) will withhold erdafitinib treatment, with at least weekly assessment of serum phosphate levels until it returns to less than 7.00 mg/dL (<2.25 mmol/L) while initiating treatment with a phosphate binder such as sevelamer (see [Table 8](#) for detailed guidelines regarding further treatment).
- Subjects with serum phosphate levels between 7.00 to 8.99 mg/dL (2.25 mmol/L to 2.90 mmol/L) should increase the erdafitinib dose to 9 mg once daily, while concurrently initiating treatment with a phosphate binder such as sevelamer (see [Table 8](#) for details).
- Subjects with serum phosphate level less than 7.00 mg/dL (<2.25 mmol/L) will increase the erdafitinib dose to 9 mg once daily without concomitant phosphate binder such as sevelamer.

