3.3. Dose-Limiting Toxicity Evaluation and Determination of RP2D

During Phase 1b, subjects will be entered in group at each dose level based on the mTPI-2 method ([Guo 2017](#)). After the last subject in each group (minimum of 3 DLT evaluable subjects) has completed the DLT observation period or developed a DLT, the SET will evaluate all available safety data and make the decision whether to escalate, stay at the current dose or de-escalate the

dose cohort with the second group of subjects treated, based on the guidelines outlined in and in the SET charter. Based on emerging clinical data, the SET might decide to include additional cohorts or terminate individual cohorts if deemed necessary. No intra-subject dose escalations will be allowed throughout this study.

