3.1.2. Phase 2: Erdafitinib +/- Cetrelimab Cohort

An overview of the Phase 2 dose expansion cohort is described in [Figure 3](#).

In Phase 2 (dose expansion), approximately 90 subjects with metastatic or locally advanced urothelial cancer with select FGFR gene alterations based on molecular testing who meet the definition of cisplatin-ineligible and have not had prior systemic therapy for metastatic disease will be stratified by ECOG PS (0-1 versus 2) and then assigned randomly (1:1 ratio) to either the erdafitinib monotherapy treatment (Arm A), or the combination treatment of erdafitinib and cetrelimab (Arm B). To further characterize safety and clinical activity of the erdafitinib and cetrelimab (Arm B).

A DRC will be commissioned for Phase 2 of this study. Based on emerging safety data, on 12 May 2020, the DRC recommended to remove the requirement for up-titration from the erdafitinib + cetrelimab combination. The DRC also made a recommendation to close Dose level 2 in Phase 1b and focus enrollment efforts into the Phase 2 part of the study. Therefore, Arm B will no longer include up-titration for erdafitinib.

Refer to [Section 11.10](#) of the main body of the protocol and the DRC charter for details regarding the composition and scope of the DRC.

Refer to [Appendix 3 Table 3](#) for an overview of the Phase 2 dosing administration of erdafitinib and cetrelimab.

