Appendix 3 Table 3: Erdafitinib and Cetrelimab Administration: Dose Arms A and B

Phase	Dosing Arms	Erdafitinib (oral administration)	Cetrelimab (IV infusion)
2	Arm A	8 mg-up-titrated to 9 mg once daily	Not administered
2	Arm B	RP2D of Phase 1b 8 mg (no up-titration) once daily	240 mg Q2W- starting at Cycle 1 480 mg Q4W starting at Cycle 5

In Arm B, if a subject permanently discontinues 1 of the study drugs, the subject may continue to receive the other study drug if investigator believes that the subject derives clinical benefit upon consultation with the sponsor's responsible medical monitor. Communication with the sponsor's

responsible medical monitor including the final decision must be documented and retained in the sponsor's trial master file and in the investigator's study files.

If a \geq Grade 3 AE is not attributable to study treatment (erdafitinib or cetrelimab), or the disease under study, then all study drugs should be held. If the event resolves to Grade 1 or baseline within 4 weeks, erdafitinib may be reintroduced at one dose level lower. If the same toxicity does not recur or worsen within 4 weeks after re-starting erdafitinib, then cetrelimab may be reintroduced at the same dose. Following re-introduction of both study drugs, if the same AE recurs at \geq Grade 3 or there is a second incidence of a \geq Grade 3 event that is not attributable to erdafitinib, cetrelimab or the disease under study, both study drugs should be discontinued.

Guidance for the management of toxicity associated with erdafitinib or cetrelimab, is provided in Sections [6.2](#) and [6.3](#), respectively.

For more information regarding the following sections, please refer to the main body of the protocol.	Page #
Section 6.2 Administration of Erdafitinib	Page 80
Section 6.3 Administration of Cetrelimab	Page 91
Section 6.4 Administration of Platinum Chemotherapy	Page 101
Section 6.5 Toxicity Due to One Study Drug and Continuation of Treatment	Page 101
Section 7 Treatment Compliance	Page 101
Section 8 Concomitant Therapy	Page 102
Section 9 Study Evaluations	Page 105
Section 9.1 Study Procedures	Page 105
Section 9.2 Efficacy Evaluations	Page 108
Section 9.3 Pharmacokinetics and Immunogenicity	Page 110
Section 9.4 Pharmacodynamic Evaluations	Page 111
Section 9.5 Predictive and Exploratory Biomarkers	Page 111
Section 9.6 Safety Evaluations	Page 113
Section 9.7 Sample Collection and Handling	Page 117

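### Section 8.3 allows erdafitinib up to 9 mg after certain inhibitors are stopped, with no limit by cohort, and so conflicts with the 8 mg, no-up-titration regimen of Phase 2 Arm B and the platinum cohort

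*Protocol*

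**What the plan says.** Section 8.3 of the protocol covers precautions with concomitant medication. For strong CYP3A4 and moderate CYP2C9 inhibitors it advises looking for alternatives. Where co-administration cannot be avoided, it asks for close monitoring and for dose modification to be considered. It then deals with the end of co-administration. Once a strong CYP3A or moderate CYP2C9 inhibitor has been stopped, the permission reads: "the erdafitinib dose may be increased up to the maximum of 9 mg daily in the absence of drug-related toxicity". No cohort, arm or dose level is named. All three cohort appendices send the reader back to main-body Section 8 for concomitant therapy, so the sentence applies throughout the study.

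Other current text fixes the erdafitinib dose more tightly:

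- Section 6.2.1: "There is no up-titration in either of the erdafitinib + cetrelimab + platinum (cisplatin or carboplatin) chemotherapy cohort or Arm B".
- Appendix 3, Section 3.1.2: "Therefore, Arm B will no longer include up-titration for erdafitinib". Appendix 3 Table 3 gives the Arm B dose as "RP2D of Phase 1b 8 mg (no up-titration) once daily".
- Synopsis, platinum cohort: "the doses of erdafitinib (8 mg daily, no up-titration) and cetrelimab (360 mg every 3 weeks [Q3W]) are constant". Appendix 2 Table 4 gives the same 8 mg dose without up-titration for all four platinum dose levels.
- Table 6 in Section 6.2.2: 9 mg appears only in the column for subjects with up-titration.
- Appendix 2, Section 3.3 (and the same section of Appendix 1): "No intra-subject dose escalations will be allowed throughout this study". Appendix 2, Section 3.1.1 repeats the rule.

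**The concern.** Take a subject in Arm B or the platinum cohort who finishes a course of a listed inhibitor and has no drug-related toxicity. Section 8.3 permits 9 mg. Section 6.2.1 and the dose tables hold the subject at 8 mg. Two sites could treat identical subjects differently and each cite the protocol.

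In Arm B this bears on what the arm measures. Section 1.5.2 records that the DRC recommended removing the up-titration requirement there, to explore whether flat 8 mg dosing would reduce interruptions and dose reductions. Safety is part of the primary Phase 2 objective, and a second route to 9 mg blurs the exposure to which Arm B adverse events are attributed. In the platinum cohort, a rise during the DLT period would leave a toxicity counted against a regimen that the subject was no longer taking.

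**Working it through.** No power, alpha or sample-size figure is involved. The check compares the Section 8.3 ceiling with the highest erdafitinib dose assigned to each regimen, and then asks whether any other rule settles the difference.

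**Step 1. Ceiling against assigned dose.**

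| Regimen | Highest assigned dose | Where stated | Section 8.3 ceiling | Gap |
|---|---|---|---|---|
| Phase 2 Arm B | 8 mg | Section 6.2.1; Appendix 3, Section 3.1.2 and Table 3 | 9 mg | 9 − 8 = 1 mg |
| Platinum DL2C, DL2C1, DL2D, DL2D1 | 8 mg | Synopsis; Section 6.2.1; Appendix 2 Table 4 | 9 mg | 9 − 8 = 1 mg |
| Arm A, DL2, DL2B | 9 mg | Section 6.2.1; Appendix 1 Table 4; Appendix 3 Table 3 | 9 mg | none |

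The relative size of the gap is 9/8 = 1.125, or 12.5% above the assigned dose.

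**Step 2. Does Section 8.3 only restore a lowered dose?** It does not require that a dose was lowered. Modification during co-administration is something to consider, so a subject may have stayed at 8 mg throughout. Section 8.3 reports average exposure increases of 5% to 34% with itraconazole and 21% to 49% with fluconazole. When the inhibitor stops, that excess goes, and a subject still on 8 mg is back to the exposure of the assigned regimen. A rise to 9 mg from there is a new dose for that regimen. Even for a subject who was reduced, the stated limit is 9 mg and not the assigned 8 mg.

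**Step 3. Does another rule decide between the texts?**

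- Section 6.5 tells sites to take the most conservative adjustment, but only when several toxicities give conflicting recommendations. Section 8.3 operates in the absence of drug-related toxicity.
- Section 6.2.2 allows re-escalation to the next higher dose after a toxicity reduction, if the event has fully resolved, the subject is benefiting and the medical monitor agrees. Section 8.3 asks for none of these except absence of toxicity, and it concerns a different event.
- The introduction says that the appendices carry the detail for each dose level or arm, but it sets no order of precedence. Section 6.2.1 and Table 6 are themselves main-body text, so the conflict also lies within the main body.

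**Step 4. How far does the escalation ban reach?** It stands among the dose-level rules of Appendices 1 and 2. Appendix 3 marks its own Section 3.3 as not applicable to Phase 2, so the ban does not clearly bind Arm B. It is not absolute in Phase 1b either: DL2 and DL2B raise individual subjects from 8 to 9 mg, and Section 6.2.2 permits re-escalation. For the platinum cohort, which has no planned rise and a DLT period of two cycles (six weeks), it adds tension with Section 8.3. The main conflict does not depend on it.

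**The case against.** The best defence is that up-titration has a defined meaning here: the Cycle 1 Day 15 step governed by serum phosphate and tolerability. Stopping an interacting drug is a different event. In context, the sentence most naturally speaks of raising a dose that was lowered because of the inhibitor. It is permissive, and 9 mg may be only an outer limit. A careful reader who lets the arm-specific tables override the general text reaches a workable answer. This is a fair account of probable intent, but the sentence does not state it, and the 9 mg limit fits only the up-titrated regimens.

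Several stronger readings that a reader might infer are not supported:

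- *That the DRC took 9 mg out of the combination.* It recommended dropping the up-titration requirement in Arm B and closing DL2. DL2B, also erdafitinib plus cetrelimab, stayed open with up-titration to 9 mg.
- *That any subject stopping any CYP inhibitor is covered.* The text is confined to strong CYP3A and moderate CYP2C9 inhibitors and requires absence of drug-related toxicity.
- *That the 6 mg Phase 1b levels show the true size.* DL1 was reviewed in January 2019 without DLTs, and DL1B enrolled nobody.
- *That the rate of stomatitis reported in Section 1.8.1 measures how often this would arise.* That rate comes from ten subjects at the up-titrated dose and is not a rate of inhibitor use. Table 10 names clotrimazole and nystatin, neither of which is in Attachment 4. Fluconazole is on both inhibitor lists there, so the trigger is possible, but its frequency is not given.

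**Conclusion.** The concern holds in a limited form. Section 8.3 permits a dose 1 mg (12.5%) above the one assigned in Arm B and at all four platinum dose levels, and the protocol has no rule that resolves the conflict. This rests on the plain wording of current text and on no outside figure. It assumes only that Section 8.3 applies to every cohort, as the appendix cross-references indicate.

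The number of subjects affected is unknown, because the protocol gives no rate of inhibitor use. Nothing here shows an effect on the ORR estimate, its confidence interval or the sample size. What is at stake is consistent dosing, a clean reading of Arm B safety and, if a rise falls inside the DLT window, attribution of DLTs in the platinum cohort. A reader might infer a flat breach of the intra-subject escalation ban across the study. The ban's placement and its existing exceptions support only a tension in the platinum cohort.

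**What to change.** Reconcile Section 8.3 with the Synopsis, Section 6.2.1, Table 6, Appendix 2 (Sections 3.1.1 and 3.3 and Table 4) and Appendix 3 (Section 3.1.2 and Table 3). State one maximum erdafitinib dose for each cohort or arm after an inhibitor is stopped. Say whether the Section 8.3 increase is available in regimens without up-titration, and whether it is available during a DLT window. The sponsor decides which rule stands; this review takes no view on the dose.

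The cost is about one sentence in Section 8.3, with no new procedures or data collection.

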9. STUDY EVALUATIONS

Following Amendment 5, and after end of study data collection timepoint has been achieved, the clinical database will be closed and only SAEs must be reported through the company safety repository.

9.1. Study Procedures

9.1.1. Overview

The study is divided into Screening, Treatment, and Follow-up Phases. The Time and Events Schedule for each treatment cohort summarizes the planned frequency and timing of all assessments applicable to this study. Clinical laboratory results (except PTH) must be available and reviewed by the investigator before study drug is administered. All planned assessments on dosing days should be completed prior to the start of the infusion unless otherwise indicated in the Time and Events Schedules. Treatment decisions will be based on local laboratory results.

Based on emerging data, adjustments to the planned schedule of assessments may be made by the sponsor in order to protect subject safety. These decisions will be documented in writing and appropriately communicated to participating investigators prior to implementation.

All planned assessments, including clinical laboratory tests (except PTH) must be completed and the results reviewed prior to the start of the infusion unless otherwise indicated in the Time and Events Schedules. If multiple assessments are scheduled for the same timepoint, it is recommended that procedures be performed in the following sequence: electrocardiogram (ECG), vital signs, blood draw. Blood collections for biomarkers and PK assessments should be kept as close to the specified time as possible. Other measurements may be done earlier than specified timepoints if needed. All blood samples must be taken from a vein contralateral to the arm into which cetrelimab is infused; alternatively, the sample may be taken from a central line.

The total maximum amount of blood to be drawn from each subject is estimated to be 17 mL at Screening. The majority of the blood samples will be collected during the first 4 cycles (ie, approximately 16 weeks). The approximate maximum blood volume drawn from each subject in this study during the first 4 cycles is in the range deemed acceptable for blood donation. Repeat or unscheduled samples may be taken for safety reasons or for technical issues with the samples.

9.1.2. Screening Phase

The Screening Phase will consist of a Molecular Eligibility Screening Period and a Full-Study Screening Period.

Molecular Eligibility Screening Period

The Molecular Eligibility Screening Period starts with the signing of a molecular eligibility informed consent form (ICF) and can occur at any time prior to administration of study drug (≥ 28 days prior to administration of the study drugs). Consent for molecular screening (but not full-study screening) may be performed remotely including consent by telephone or video consultation, unless not permitted according to local guidance.

Subjects may by-pass the molecular Screening Phase of Study BLC2002 if they have already been molecularly screened for FGFR alterations by the central laboratory in the context of another Janssen-sponsored study.

Molecular eligibility will be determined for all subjects by the presence (or absence) of select FGFR mutations and fusions as described in [Table 4](#).

During the Molecular Eligibility Screening Period, there are 2 approaches that may be used to determine FGFR status for this study, ie, central molecular screening or local test results:

1) Central Molecular Screening (Submission of Tissue and Blood Samples Required*)

FGFR analysis of tissue and blood by the central laboratory. Archival tumor tissue or a fresh biopsy sample and a blood sample will be sent to the central laboratories for testing. Blood and tissue samples do not need to be submitted concurrently; samples may be submitted as they become available during the Molecular Eligibility Screening Period. The central laboratory will evaluate subjects for molecular eligibility (where applicable) by analyzing tumor and blood specimens for the presence of select FGFR mutations and gene fusions. The sponsor or central laboratory/designee will communicate results of the molecular testing to the site. If a biopsy is required to perform FGFR analysis, the subject must consent to this procedure utilizing the main study consent form.

Subjects may enroll in the study if at least one sample (tissue or blood) results in identification of a study-eligible FGFR alteration, however if a subject enrolls based on blood testing, a tissue sample must be submitted for central confirmatory testing.

2) Local report with evidence of a study-eligible FGFR mutation or fusion (or for Phase 1b erdafitinib + cetrelimab + platinum (cisplatin or carboplatin) chemotherapy cohort proof of FGFR testing, independent of FGFR status). Local test results (from tissue or blood) or the Qiagen Therascreen FGFR RGQ RT-PCR test (from tissue) performed at a CLIA-certified or regional equivalent laboratory may be used to meet molecular eligibility. A copy of the test report documenting the FGFR result must be included in the subject records and a de-identified copy must also be submitted to the sponsor for confirmation of eligibility.

- If a subject is enrolled based on local testing, a tissue and blood sample must still be submitted at the time of enrollment for retrospective confirmation of FGFR status, diagnostic development, and biomarker research. If tissue specimens are not available for retrospective confirmation testing, the site should contact the sponsor prior to proceeding to full-study screening.

- The sponsor cannot authorize performance of high-risk fresh biopsies to obtain tissue for retrospective central confirmation of FGFR status.
- The results of retrospective central confirmation do not affect the subject's eligibility for the study. Results of retrospective confirmation studies will not be communicated to the site. Concordance between local and central testing, where applicable, will be reviewed periodically by the sponsor.

If a subject meets the molecular eligibility criteria (where applicable), he or she may continue study screening under the Full-Study ICF for determination of full-study eligibility.

Full-Study Screening Period

The Study Screening Period (for full-study eligibility) is within 28 days before the first dose of study medication with the exception of the screening disease assessments which may be done within 35 days prior to C1D1. Subjects must meet all the inclusion criteria and none of the exclusion criteria in Section 4. Retesting of abnormal laboratory values that may lead to exclusion will be allowed once. To reassess eligibility, retesting will take place during an unscheduled visit in the Screening Phase.

